5.4.3 Automated Alerts - INTERVENTION SITES ONLY

Each time a patient self-reports an issue of a concerning level or that increases from the prior self-report, an automatic email alert notification will be triggered to the site CRA. The alert will only include the participant's study ID, not their identifying information. The CRA will be responsible for adding the patient's name, medical record number, and contact information to the email, then forwarding the email to the appropriate site clinical nurse caring for the patient immediately upon receipt, with a CC to the Nurse Champion. These alert notifications will include a link to evidence-based symptom management pathway recommendations when applicable that can be quickly and easily referenced by the nurse.

5.4.4 CRA Follow Up of Nurse Actions Taken in Response to Alerts - INTERVENTION SITES ONLY (Form C11)

Within 72 hours of each alert, the CRA should contact the nurse to ascertain what action(s) was taken in response to the alert using the "Nursing Alert Response Form" (Form C11). This form offers several options that should be asked or printed

or pasted into an email and given to the nurse as choices (below), and the nurse's response should be used by the CRA to complete Form C11.

Was the patient contacted?

- Yes
- No

How was the patient contacted (select all that apply)?

- In person
- By phone or text
- By email
- By patient portal

If by phone, did you leave a voicemail?

- Yes
- No

Select any discussion that occurred (select all that apply):

- Discussed symptom with patient
- Discussed symptom with caregiver
- Discussed with other clinician(s)

Select any action/advice that occurred (select all that apply):

- Supportive medication – prescribed or modified dose/schedule (e.g., anti-emetic)
- Patient will use over-the-counter (OTC) medication at home (e.g., analgesic, Senna)
- Chemotherapy - dose changed or held
- Sent to emergency room/urgent care/admitted to hospital
- Imaging or laboratory test ordered
- Appointment made to come in to clinic for evaluation
- Referral made to another clinic
- Patient will use self-management strategies at home (e.g., meditation, walking)

Select reason if no action/advice occurred (select all that apply):

- Already aware of symptom, so no action taken
- Symptom resolved itself
- Symptom unrelated to chemo (e.g., cold symptoms)
- Will discuss with patient during next visit

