The number of alerts, reasons for the alerts, patient and nurse opinions regarding the urgency of an alert, and immediate nurse actions in response to an alert will be tabulated descriptively. To predict the nurse's opinion regarding the urgency of an alert, a generalized linear mixed model with a logit link will be employed with fixed effects for patient characteristics at baseline and information from the weekly PRO surveys (e.g., patient-reported symptoms, worsening of each symptom from the prior week, and prior receipt of an alert for each symptom) and a random patient intercept. To assess the added benefit of the weekly PRO surveys, results will be compared to those from a generalized linear mixed model with baseline patient characteristics (only) as fixed effects. Receiver operating characteristic (ROC) curves will be plotted along with computed areas-under-the-curve. Sensitivity, specificity, positive predictive value, and negative predictive value will be estimated with 95% Wald confidence intervals for various cutpoints (e.g., cutpoint for likelihood of an alert being urgent that achieves 80% sensitivity).

In March 2019, a monthly financial toxicity question was added to the weekly PRO surveys completed by patients at PRO practices. Financial difficulties were also measured for all patients (both arms, entire study) using a single item from the EORTC QLQ-C30. Baseline financial difficulties (as measured by the EORTC QLQ-C30) will be tabulated overall and by arm, and the relationship between financial difficulties and patient characteristics will be explored using chi-square tests for categorical variables and Wilcoxon Rank Sum tests for continuous variables. The proportion of patients with any new/worsening financial difficulties (as measured by the EORTC QLQ-C30) will be compared between arms using a generalized linear mixed model with fixed effects for arm and a random practice intercept term to account for clustering by practice. This analysis will be completed using all patients with data, as well as in the subset of patients who participated during the time in which a financial toxicity question was administered in the PRO arm and the subset of patients who participated entirely before the time in which a financial toxicity question was administered in the PRO arm.

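### The alert-urgency analysis has no practice term and leaves interval variance, prediction type and validation unstated: precision is likely overstated and the bias in added benefit is uncontrolled

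*SAP*

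**What the plan says.** SAP 3.6.3 predicts the nurse's opinion of urgency with a logit mixed model on baseline characteristics and weekly survey data. The list of terms ends with "prior receipt of an alert for each symptom) and a random patient intercept". No practice or nurse term appears.

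The evaluation has three parts:
- **Comparison:** "To assess the added benefit of the weekly PRO surveys, results will be compared to those from a generalized linear mixed model" containing baseline characteristics only.
- **Discrimination:** "Receiver operating characteristic (ROC) curves will be plotted along with computed areas-under-the-curve".
- **Classification:** "Sensitivity, specificity, positive predictive value, and negative predictive value will be estimated with 95% Wald confidence intervals for various cutpoints", the example being a "cutpoint for likelihood of an alert being urgent that achieves 80% sensitivity".

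Elsewhere the SAP allows for practice. In the same section the financial-difficulties model is a "generalized linear mixed model with fixed effects for arm and a random practice intercept term to account for clustering by practice". The mixed and responder models in 3.6.3 and the mixed subgroup models in 3.8 also carry a random practice intercept.

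On where the data come from, Protocol 5.4.3 triggers an alert "Each time a patient self-reports an issue of a concerning level or that increases from the prior self-report", on weekly surveys that run for up to a year. Under Protocol 5.4.4, "the CRA should contact the nurse to ascertain what action(s) was taken in response to the alert".

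**The concern.** The outcome is a judgement made by nursing staff at the practice. The Form C11 options printed in Protocol 5.4.4 include no urgency scale, so local thresholds for calling an alert urgent are plausible. A patient intercept can absorb some of that variation, but it still treats patients at the same practice as independent.

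Sensitivity, specificity and predictive values are proportions taken over alerts. A random effect in the prediction model does not by itself enter their variance. An ordinary Wald interval would count every alert as independent, although patients and practices each contribute many.

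The AUC comparison has a separate weakness. The larger model contains the smaller one. Without held-out data or an optimism correction, the analysis cannot tell real information in the weekly items from overfitting. What is at stake is the trial's statement about how far weekly surveys improve prediction of urgent alerts, and how precisely that is known.

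**Working it through.** **No figure to reproduce.** The documents give no alert count, urgency rate, AUC or interval width for this analysis. The only practice ICCs they give are 0.001 (survival) and 0.055 (physical function), both in SAP 2.6. Those inputs reproduce the stated design power. For physical function with 1,000 patients at 50 practices and 85% evaluable, there are 17 per practice, the design effect is 1 + 16 × 0.055 = 1.88, and power is 95.5% (stated 95%). For survival with 576 events, power is 90.3% (stated at least 90%). I use the two ICCs as end points for an unknown urgency ICC.

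**Clusters.** Alerts arise only at intervention sites. With 1,200 patients at 52 practices allocated 1:1, that is about 600 patients at 26 practices, so n = 600/26 = 23.08 patients per practice.

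**Interval width.** Let m be alerts per patient. Assume correlation r_patient + r_practice for two alerts from one patient, and r_practice for alerts from different patients at one practice.

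DE = 1 + (m − 1)(r_patient + r_practice) + (n − 1) × m × r_practice

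The width ratio is √DE, and the coverage of a naive 95% interval is 2Φ(1.96/√DE) − 1.

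Example: m = 10, r_patient = 0.3, r_practice = 0.055 gives 1 + 9 × 0.355 + 22.08 × 10 × 0.055 = 16.34.

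| m | r_patient | r_practice | DE | Width ratio | Naive coverage |
|---|---|---|---|---|---|
| 3 | 0.1 | 0.001 | 1.27 | 1.13 | 92% |
| 10 | 0.3 | 0.001 | 3.93 | 1.98 | 68% |
| 10 | 0.3 | 0.01 | 6.00 | 2.45 | 58% |
| 10 | 0.3 | 0.055 | 16.34 | 4.04 | 37% |
| 20 | 0.3 | 0.055 | 32.03 | 5.66 | 27% |

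If the interval already allowed for repeated alerts within patient, adding practice would widen it 1.02 to 1.07 times at ICC 0.001, 1.19 to 1.56 times at 0.01 and 1.8 to 2.7 times at 0.055.

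**Sensitivity is less affected.** It uses urgent alerts only. If 15% are urgent (assumed), 10 alerts per patient become 1.5. With r_patient = 0.3:
- r_practice = 0.055: DE = 1 + 0.5 × 0.355 + 22.08 × 1.5 × 0.055 = 3.00, width ratio 1.73, coverage 74%.
- r_practice = 0.001: DE = 1 + 0.5 × 0.301 + 22.08 × 1.5 × 0.001 = 1.18, width ratio 1.09, coverage 93%.

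This takes clusters as equal in size; unequal clusters would make it worse.

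**Added benefit.** A simulation used 12 baseline and 36 weekly predictors, about 15% urgent alerts and a random patient intercept. It compared the AUC gain on the fitting data with the gain in new practices.

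| Alerts per patient | Fitting data, fixed-effect prediction | Fitting data, patient-specific prediction | New practices |
|---|---|---|---|
| 3 | 0.075 | 0.003 | 0.038 |
| 10 | 0.064 | 0.015 | 0.053 |
| 20 | 0.056 | 0.018 | 0.059 |

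When the weekly items carried no information, the fixed-effect gain on the fitting data was still +0.036, +0.014 and +0.007, against −0.025, −0.012 and −0.007 in new practices. Across these simulations, cluster-robust standard errors for the classification measures were about 1.1 to 5.3 times the naive ones.

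**The case against.** The strongest reply is that much of this rests on silence. Wald names the form of an interval and is compatible with a cluster-robust variance, and nothing in the SAP excludes cross-validation. The model does account for repeated alerts in its fit. Alert notification is only an additional endpoint (SAP 3.6.1), explored rather than tested between arms (SAP 2.2.1). All of that stands. It makes the criticism one of under-specification, except for the missing practice term, which is in the text.

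A reader might also infer more than the documents support:
- **That the benefit of weekly surveys is overstated.** The SAP does not say whether the AUC uses fixed-effect or patient-specific predictions. In the simulation the first inflated the gain when alerts were few, and the second understated it.
- **That alerts at a practice share a rater.** Protocol 3.5 has nurses designated patient by patient, so a site may have several. A common local threshold is plausible; a common rater is not documented.
- **That the analysis will set alert cutpoints.** The SAP only reports accuracy at several.
- **That models and cutpoints will be judged on the data that fitted them.** This is the natural reading, but it is not stated.

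**Conclusion.** The point holds as a minor one. The practice level is missing from this model although ratings come from nurses within practices and neighbouring models include it. The interval variance, the type of prediction and the validation are unspecified.

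If ordinary Wald intervals are used, precision is overstated under every assumption tried: by a factor of 1.13 to 5.7 in width for proportions over all alerts, and by less for sensitivity. The wide end needs many alerts and a practice ICC as high as that for physical function. At ICC 0.001 nearly all the effect comes from repeated alerts within patients. The ICC that matters is that of correct classification, which the documents do not give, so no single value in the range should be quoted as the likely one.

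The bias in the apparent added benefit is uncontrolled, and its size and direction cannot be determined from the plan. The primary and key secondary analyses are not touched.

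**What to change.** In the alert paragraph of SAP 3.6.3:
1. Add a random practice intercept to both the full and the baseline-only model, keeping the patient intercept.
2. Obtain intervals for AUC, sensitivity, specificity and predictive values from a bootstrap that resamples whole practices.
3. State that AUCs and cutpoint performance use fixed-effect predictions, estimated by leave-practices-out cross-validation with cutpoints chosen in the training practices.
4. Compare the two models on the held-out predictions, and report the AUC difference with its practice-level bootstrap interval.

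No new data are needed. The cost is a little more programming, wider intervals and possibly a lower AUC.

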### 3.6.4. Sensitivity analyses for secondary endpoints

As described above, supplemental analyses will include mean and responder comparisons at time points other than 3 months. For the responder analysis, a 10-point change will also be applied to ensure results remain consistent with a higher threshold. Finally, impact of the COVID pandemic will be explored by repeating key between-arm analyses within the subset of patients enrolled prior to December 1, 2019 (date selected to ensure that the 3-month time point occurred prior to widespread COVID pandemic impacts on clinical practices in the US). Outcomes of patients enrolled after December 1, 2019, may also be tabulated and compared to outcomes of patients enrolled prior to December 1, 2019.

## 3.7. Safety endpoint evaluation

### 3.7.1. Safety endpoints

As the intervention is the administration of questionnaires, no safety data will be collected as part of this study. See Section 3.6.3 for analysis describing patient adherence to the intervention.

months). Additional subgroup analyses may be carried out for other time points and/or other EORTC QLQ-C30 scales as indicated though care will be taken to note inflation of type I error when incorporating additional analyses. To carry out subgroup analyses, a general linear mixed model within each level of the subgroup variable will be fit using data from all time points (months 0, 1, 3, 6, 9, and 12), and effect of the intervention at month 3 will be tested similar to the primary analysis using a linear combination of model parameters. Such values as the mean change from baseline at 3 months by arm, and difference in mean change from baseline at 3 months between arms will be estimated with confidence intervals based on these mixed models. Next, a general linear mixed model will be fit including all patients and including fixed effects for arm, time point, and the given subgrouping variable, as well as pairwise interactions between arm and time point, arm and subgroup variable, and time point and subgroup variable. Higher order interactions will initially be included in models but may be omitted if lacking statistical significance. A random practice intercept term will account for clustering by practice. Repeated observations by patient will be modeled using compound symmetric correlation structure over time. The Type 3 test of the interaction effect between arm and the given subgroup variable will be used to formally test for statistically significant subgroup effect. The value(s) of the coefficient(s) on the interaction effect between arm and subgroup will be used to assess the magnitude of the interaction. A similar approach as described above but using Cox regression will be used for subgroup analysis of overall survival. Regression will be carried out within each level of a subgroup variable and carried out across levels with a subgroup-by-arm interaction term to formally test for statistically significant subgroup effect.

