## 2.6. Power

For overall survival, the trial’s initial sample size of 1,000 patients from 50 U.S. practices provided 80% power for a hazard ratio of 0.76 (based on the prior single-center randomized controlled trial) which is considered clinically meaningful (Sobrero AF, et al. 2015; Ellis LM, et al. 2014) using a two-sided alpha=0.05/2 log-rank test with 521 events observed during the observation period, computed using the formula by Xie and Waksman, 2003, with an intracluster correlation coefficient of 0.001 (estimated from the 10 largest legacy Alliance trials involving 12,717 total patients). This sample size also provided 95% power to measure the established clinically meaningful difference of 0.37 standard deviations on the QLQ-C30 Physical Function Scale based on a prior single-center randomized controlled trial (~9 points on the 100-point QLQ-C30 scale) between randomization groups using a two-sided alpha=0.05/2 t-test assuming an intracluster correlation coefficient of 0.055 (Adams G, et al. 2004), and assuming that 85% of patients are evaluable for the primary analysis at the 3-month time point.

In order to optimize power, the sample size was subsequently amended to 1,200 patients from 50 (+/-5) U.S. practices. Power for comparing physical functioning increased to 96-97% and power remained 80% for comparing overall survival under the assumption that statistical analysis would be conducted after 522 events. Each analysis would be undertaken with a two-sided alpha=0.05/2.

Finally, after an additional amendment to increase type I error for the overall survival analysis, with a total of 1,200 patients at 52 practices nationally, there was at least 90% power for a hazard ratio of 0.76 (based on the prior single-center randomized controlled trial) which is considered clinically meaningful using a two-sided alpha=0.05 log-rank test with 576 observed events, computed using the formula by Xie and Waksman, 2003, with an intracluster correlation coefficient of 0.001 (estimated from the 10 largest legacy Alliance trials involving 12,717 total patients). This power calculation further assumes drop-out of 150 patients in the first 2.5 years.

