#### 3.6.3. Analyses of secondary and exploratory endpoints

Mean change from baseline in physical function, symptom control, and HRQL at 3 months will be compared between arms using a linear combination of parameters from a general linear mixed model. Each model will include all available data from all time points (months 0, 1, 3, 6, 9, and 12). Fixed effects will include arm, time point, cancer type, and arm-by-time point interaction. A random practice intercept term will be included to account for clustering by practice. Repeated observations by patient will be modeled using compound symmetric correlation structure over time. Such values as the mean change from baseline at 3 months by arm, and difference in mean change from baseline at 3 months between arms will be estimated with confidence intervals based on the mixed model. Comparisons at other time points will also be carried out and graphically displayed using mean plots.

To supplement comparison of means, a responder analysis will also be employed. Patients who complete the QLQ-C30 at baseline and at 3 months will be categorized as improving on each outcome (physical function, symptom control, HRQL) if their score increased by 5 or more points from baseline; worsening if their score decrease by 5 or more points from baseline; and otherwise as stable. The selection of a 5-point change on the 100-point QLQ-C30 scale was selected as clinically meaningful based on work by Cocks K, et al. 2012. The proportion of patients with improvement, stability, or worsening will be compared between arms at 3 months using a cumulative logistic regression model with fixed effects for arm and cancer type and a random practice intercept term to account for clustering by practice.

Similar to the mean comparisons, the responder analysis will be carried out at other time points as needed to supplement that primary analysis at 3 months.

See Section 3.5.3 for statistical analysis combining physical function, symptom control, and HRQL with overall survival data to be conducted at time of overall survival analysis.

Patient adherence (feasibility) to the intervention (i.e., completion of the weekly symptom surveys) is defined at each week as the proportion of participating patients completing a survey divided by the number of participating patients who are expected to complete a survey. Completion will be computed at each week and overall.

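### For QLQ-C30 outcomes, the subgroup test and effect size in SAP 3.8 do not target the 3-month change from baseline that is reported for each subgroup

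*SAP*

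**What the plan says.** SAP 3.8 (Subgroups) handles QLQ-C30 outcomes in two steps.

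- **Within each level.** A mixed model is fitted to months 0, 1, 3, 6, 9 and 12, and the "difference in mean change from baseline at 3 months between arms will be estimated with confidence intervals based on these mixed models".
- **Pooled model.** It contains arm, time point, the subgroup variable and all pairwise interactions. On the three-way term: "Higher order interactions will initially be included in models but may be omitted if lacking statistical significance". On testing: "The Type 3 test of the interaction effect between arm and the given subgroup variable will be used to formally test" for a subgroup effect. On size: "The value(s) of the coefficient(s) on the interaction effect between arm and subgroup will be used to assess the magnitude of the interaction".

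The parent analysis in SAP 3.6.3 has the same six response visits, no baseline-score covariate, and an effect at 3 months that "will be compared between arms using a linear combination of parameters from a general linear mixed model". Nowhere does the SAP name the three-way term, or a month-3 contrast by subgroup, as the subgroup test or effect size.

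**The concern.** The estimates shown for each subgroup concern change from month 0 to month 3. The p-value that declares a subgroup effect, and the number that sizes it, come from a term that is not specific to month 3 and does not subtract baseline. A reader would take the p-value as a test of whether the displayed estimates differ, and it is not one. Two analysts using different reference visits could also report different magnitudes from the same fitted model. SAP 3.8 lists fifteen subgroup variables, and the rule applies to physical function at 3 months, which is the key secondary endpoint, as well as to other QLQ-C30 scales.

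**Working it through.** **Scale, from the plan's own power figure.** SAP 2.6 gives 0.37 SD, about "9 points on the 100-point QLQ-C30 scale", two-sided alpha 0.025, ICC 0.055, and power calculated "assuming that 85% of patients are evaluable for the primary analysis at the 3-month time point".

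- N = 1,000, 50 practices: 425 evaluable per arm, 17 per practice. Design effect 1 + 16 × 0.055 = 1.88. Effective n per arm 425 / 1.88 = 226. Then 0.37 × √(226/2) − 2.241 = 1.69, so power is 95.5% (stated: 95%).
- N = 1,200, 50 practices: the same steps give 96.9% (stated: 96-97%).

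The plan's figure reproduces, and the implied SD is 9 / 0.37 = 24.3 points.

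**Algebra (needs no assumed numbers).** Let δ(t) be the arm difference in one subgroup level minus that in the other, at visit t. The reported effects differ between levels by θ = δ(3) − δ(0).

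- *Three-way term kept:* the usual Type 3 hypothesis is that the mean of the six δ(t), weight 1/6 each with month 0 included, is zero. With reference-cell coding the coefficient is δ at the reference visit alone.
- *Three-way term dropped:* δ(t) is one constant, so θ is forced to 0. The coefficient is a weighted mean of the six visits. The weights are equal with complete data and lean towards month 0 with dropout.

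**Assumptions for size (not in the documents).** Two-level subgroup; 260 patients per arm-by-level cell (52 practices × 20 / 4); compound symmetry with correlation r = 0.4, 0.6, 0.8; two-sided 0.05; no practice effect in the formulas. With SD = 1:

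- Var(six-visit mean) = (4/260) × (1 + 5r)/6
- Var(month 3 minus month 0) = (4/260) × 2(1 − r)

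At r = 0.6 the standard errors are 0.1013 and 0.1109. For 9 points at month 3 only, the named test has z = (0.37/6)/0.1013 = 0.61 and the contrast has z = 0.37/0.1109 = 3.34. For 9 points constant after baseline, the named test has z = (0.37 × 5/6)/0.1013 = 3.04.

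| True subgroup difference | Data | Named test, three-way kept (r = 0.4 / 0.6 / 0.8) | Month 3 − month 0 contrast |
|---|---|---|---|
| 9 points, month 3 only | complete | 11 / 9 / 8.5% | 78 / 92 / 99.7% |
| 9 points, constant after baseline | complete | 94 / 86 / 78% | 78 / 92 / 99.7% |
| 9 points, month 3 only | dropout | 10 / 9 / 8% | 73 / 88 / 99% |
| 9 points, constant after baseline | dropout | 91 / 83 / 76% | 73 / 88 / 99% |
| 5 points, constant after baseline | complete | 50 / 39 / 33% | 33 / 46 / 75% |

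Dropout means 85% retained at month 3 (SAP 2.6), with 100, 95, 70, 60 and 50% assumed at months 0, 1, 6, 9 and 12. Five points is the responder threshold in SAP 3.6.3, used here only as a smaller size: 0.37 × 5/9 = 0.206 SD.

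**Coefficient when the true difference is 9 points.**

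| Model | Month 3 only | Constant after baseline |
|---|---|---|
| Kept, reference month 0 | 0 | 0 |
| Kept, reference month 3 | 9 | 9 |
| Kept, reference month 12 | 0 | 9 |
| Dropped, complete data | 1.5 | 7.5 |
| Dropped, assumed dropout | about 1.6 | 6.6-6.7 |

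In the last row month 0 carries weight 0.25-0.27 and month 12 about 0.09.

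**How often the three-way term would be dropped (5 df, complete data).** At 9 points it is non-significant in about 22 / 7 / 0.1% of trials. At 5 points it is non-significant in about 72 / 59 / 26%.

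**Uneven subgroup (10/90 split), r = 0.6, complete data, 9 points.** Month 3 only: 6.5% versus 52%. Constant: 45% versus 52%.

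**Simulation check.** 600 trials per scenario, 52 practices of 20, ICC 0.055, the assumed dropout, r = 0.6. Entries are named test with term kept / named test with term dropped / contrast:

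- 9 points, month 3 only: 9.5 / 9.8 / 89.3%
- 9 points, constant: 87.7 / 78.0 / 90.5%
- 5 points, month 3 only: 5.7 / 6.8 / 42.0%
- null: 4.0 / 4.7 / 4.8%

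**The case against.** The strongest reply is that little depends on this. The SAP already shows the month-3 difference in change with a confidence interval for each level, and for a two-level subgroup a reader can roughly subtract one from the other. That stands and limits the consequence, but the SAP still designates the mismatched p-value as the formal test.

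Second, an effect at month 3 and at no other visit is an extreme pattern for an intervention delivered weekly for up to a year. That is fair: the large power loss belongs to differences concentrated at month 3. For a difference constant after baseline, setting the two z-values equal gives (25/6)/(1 + 5r) = 1/[2(1 − r)], so r = 0.55, and below that the named test is the more powerful. It still tests a different quantity, and the coefficient problem occurs in both patterns.

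Third, higher-order terms are included at first. This does not help, because the named test and coefficient remain the two-way ones even when those terms stay.

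Fourth, the pooled-model sentence does not repeat the visit list, so month 0 as a response there is an inference. It is well supported: the within-level model described just before it and SAP 3.6.3 both list month 0, and neither adjusts for baseline score.

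Finally, 1,200 patients would give 300 per cell rather than 260. At r = 0.6, 9 points constant, that gives 91% versus 95%, so the direction is unchanged.

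**Conclusion.** The concern holds. For QLQ-C30 outcomes the named subgroup test and magnitude do not correspond to the effects reported beside them, and this follows from the model as written. How much it matters depends on the unknown time pattern and within-patient correlation. The named test largely misses a subgroup difference concentrated at month 3 (about 8-11% power under the 50/50 assumptions above). For one that is constant after baseline it ranges from stronger than the matching contrast to clearly weaker. The coefficient for a true 9 points can be anything from 0 to 9 depending on coding and on whether the three-way term is kept.

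A systematic arm-by-subgroup gap already present at baseline would be counted as effect modification. The documents report no such gap, and chance imbalance does not inflate the unconditional type I error.

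The within-level estimates are sound. The Cox subgroup test for overall survival is not affected, because its interaction term matches the hazard ratios reported. No primary conclusion changes. This should be corrected before QLQ-C30 subgroup findings are interpreted.

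**What to change.** In SAP 3.8, define both the formal subgroup test and the magnitude for QLQ-C30 outcomes as the arm-by-subgroup-by-time contrast for month 3 minus month 0, with a confidence interval, and always keep the three-way term in that model. State the downside: if the difference is constant after baseline and the correlation is low, some power is lost (78% versus 94% at 0.4, 9 points, complete data).

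The cost is one contrast statement in the SAP and the program, with no new data. The change is post hoc, because the SAP's revision table and reference list show that the secondary outcomes had already been published. Record it as such in SAP section 4. Show the contrast beside any two-way tests already run, and state the coding of those models and whether the three-way term was kept.
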